**Table 74: T Cell Memory Responses by CyTOF – Per Protocol Population**

**Table 75: Correlation of Serum IgA GMFR vs Fecal dmLT-specific IgA GMFR by Time Point and Treatment Group, Immunogenicity Population**

Time Point	Spearman Correlation (95% CI)							
	Cohort A: Oral 5 µg dmLT (N=X)	Cohort B: Oral 25 µg dmLT (N=X)	All Oral Cohorts: Placebo (N=X)	Cohort C: Sublingual 5 µg dmLT (N=X)	Cohort D: Sublingual 25 µg dmLT (N=X)	All Sublingual Cohorts: Placebo (N=X)	Cohort E: Intradermal 0.3 µg dmLT (N=X)	Cohort E: Intradermal Placebo (N=X)
Max Any Time Post Dose 1	x.xx (x.xxx-x.xxx)	x.xx (x.xxx-x.xxx)	x.xx (x.xxx-x.xxx)	x.xx (x.xxx-x.xxx)	x.xx (x.xxx-x.xxx)	x.xx (x.xxx-x.xxx)	x.xx (x.xxx-x.xxx)	x.xx (x.xxx-x.xxx)

Tables with similar format:

**Table 76: Correlation of Serum IgA GMFR vs Fecal dmLT-specific IgA GMFR by Time Point and Treatment Group, Per Protocol Population****Table 77: Correlation of Serum IgA GMFR vs Fecal dmLT-specific/Total IgA GMFR by Time Point and Treatment Group, Immunogenicity Population****Table 78: Correlation of Serum IgA GMFR vs Fecal dmLT-specific/Total IgA GMFR by Time Point and Treatment Group, Per Protocol Population**

**Table 79: Correlation of Serum IgA GMFR vs ALS IgA Titers GMFR by Time Point and Treatment Group, Immunogenicity Population**

Time Point	Spearman Correlation (95% CI)							
	Cohort A: Oral 5 µg dmLT (N=X)	Cohort B: Oral 25 µg dmLT (N=X)	All Oral Cohorts: Placebo (N=X)	Cohort C: Sublingual 5 µg dmLT (N=X)	Cohort D: Sublingual 25 µg dmLT (N=X)	All Sublingual Cohorts: Placebo (N=X)	Cohort E: Intradermal 0.3 µg dmLT (N=X)	Cohort E: Intradermal Placebo (N=X)
Max Any Time Post Dose 1	x.xx (x.xxx-x.xxx)	x.xx (x.xxx-x.xxx)	x.xx (x.xxx-x.xxx)	x.xx (x.xxx-x.xxx)	x.xx (x.xxx-x.xxx)	x.xx (x.xxx-x.xxx)	x.xx (x.xxx-x.xxx)	x.xx (x.xxx-x.xxx)

Tables with similar format:

**Table 80: Correlation of Serum IgA GMFR vs ALS IgA Titers GMFR by Time Point and Treatment Group, Per Protocol Population**

**Table 81: Correlation of Serum IgG GMFR vs ALS IgG Titers GMFR by Time Point and Treatment Group, Immunogenicity Population**

Time Point	Spearman Correlation (95% CI)							
	Cohort A: Oral 5 µg dmLT (N=X)	Cohort B: Oral 25 µg dmLT (N=X)	All Oral Cohorts: Placebo (N=X)	Cohort C: Sublingual 5 µg dmLT (N=X)	Cohort D: Sublingual 25 µg dmLT (N=X)	All Sublingual Cohorts: Placebo (N=X)	Cohort E: Intradermal 0.3 µg dmLT (N=X)	Cohort E: Intradermal Placebo (N=X)
Max Any Time Post Dose 1	x.xx (x.xxx-x.xxx)	x.xx (x.xxx-x.xxx)	x.xx (x.xxx-x.xxx)	x.xx (x.xxx-x.xxx)	x.xx (x.xxx-x.xxx)	x.xx (x.xxx-x.xxx)	x.xx (x.xxx-x.xxx)	x.xx (x.xxx-x.xxx)

Tables with similar format:

**Table 82: Correlation of Serum IgG GMFR vs ALS IgG Titers GMFR by Time Point and Treatment Group, Per Protocol Population**

**Table 83: Correlation of Fecal dmLT-specific IgA GMFR vs ALS IgA Titers GMFR by Time Point and Treatment Group, Immunogenicity Population**

Time Point	Spearman Correlation (95% CI)							
	Cohort A: Oral 5 µg dmLT (N=X)	Cohort B: Oral 25 µg dmLT (N=X)	All Oral Cohorts: Placebo (N=X)	Cohort C: Sublingual 5 µg dmLT (N=X)	Cohort D: Sublingual 25 µg dmLT (N=X)	All Sublingual Cohorts: Placebo (N=X)	Cohort E: Intradermal 0.3 µg dmLT (N=X)	Cohort E: Intradermal Placebo (N=X)
Max Any Time Post Dose 1	x.xx (x.xxx-x.xxx)	x.xx (x.xxx-x.xxx)	x.xx (x.xxx) -x.xxx	x.xx (x.xxx-x.xxx)	x.xx (x.xxx-x.xxx)	x.xx (x.xxx-x.xxx)	x.xx (x.xxx-x.xxx)	x.xx (x.xxx-x.xxx)

Tables with similar format:

**Table 84: Correlation of Fecal dmLT-specific IgA GMFR vs ALS IgA Titers GMFR by Time Point and Treatment Group, Per Protocol Population**

**Table 85: Correlation of Fecal dmLT-specific/Total IgA GMFR vs ALS IgA Titers GMFR by Time Point and Treatment Group, Immunogenicity Population**

Time Point	Spearman Correlation (95% CI)							
	Cohort A: Oral 5 µg dmLT (N=X)	Cohort B: Oral 25 µg dmLT (N=X)	All Oral Cohorts: Placebo (N=X)	Cohort C: Sublingual 5 µg dmLT (N=X)	Cohort D: Sublingual 25 µg dmLT (N=X)	All Sublingual Cohorts: Placebo (N=X)	Cohort E: Intradermal 0.3 µg dmLT (N=X)	Cohort E: Intradermal Placebo (N=X)
Max Any Time Post Dose 1	x.xx (x.XXX-x.XXX)	x.xx (x.XXX-x.XXX)	x.xx (x.XXX-x.XXX)	x.xx (x.XXX-x.XXX)	x.xx (x.XXX-x.XXX)	x.xx (x.XXX-x.XXX)	x.xx (x.XXX-x.XXX)	x.xx (x.XXX-x.XXX)

Tables with similar format:

**Table 86: Correlation of Fecal dmLT-specific/Total IgA GMFR vs ALS IgA Titers GMFR by Time Point and Treatment Group, Per Protocol Population**

**Table 87: Correlation of ASC IgA Count vs ALS IgA Titers GMFR by Time Point and Treatment Group, Immunogenicity Population**

Time Point	Spearman Correlation (95% CI)							
	Cohort A: Oral 5 µg dmLT (N=X)	Cohort B: Oral 25 µg dmLT (N=X)	All Oral Cohorts: Placebo (N=X)	Cohort C: Sublingual 5 µg dmLT (N=X)	Cohort D: Sublingual 25 µg dmLT (N=X)	All Sublingual Cohorts: Placebo (N=X)	Cohort E: Intradermal 0.3 µg dmLT (N=X)	Cohort E: Intradermal Placebo (N=X)
Max Any Time Post Dose 1	x.xx (x.xxx-x.xxx)	x.xx (x.xxx-x.xxx)	x.xx (x.xxx-x.xxx)	x.xx (x.xxx-x.xxx)	x.xx (x.xxx-x.xxx)	x.xx (x.xxx-x.xxx)	x.xx (x.xxx-x.xxx)	x.xx (x.xxx-x.xxx)

Tables with similar format:

**Table 88: Correlation of ASC IgA Count vs ALS IgA Titers GMFR by Time Point and Treatment Group, Per Protocol Population**

**Table 89: Correlation of ASC IgG Count vs ALS IgG Titers GMFR by Time Point and Treatment Group, Immunogenicity Population**

Time Point	Spearman Correlation (95% CI)							
	Cohort A: Oral 5 µg dmLT (N=X)	Cohort B: Oral 25 µg dmLT (N=X)	All Oral Cohorts: Placebo (N=X)	Cohort C: Sublingual 5 µg dmLT (N=X)	Cohort D: Sublingual 25 µg dmLT (N=X)	All Sublingual Cohorts: Placebo (N=X)	Cohort E: Intradermal 0.3 µg dmLT (N=X)	Cohort E: Intradermal Placebo (N=X)
Max Any Time Post Dose 1	x.xx (x.xxx-x.xxx)	x.xx (x.xxx-x.xxx)	x.xx (x.xxx-x.xxx)	x.xx (x.xxx-x.xxx)	x.xx (x.xxx-x.xxx)	x.xx (x.xxx-x.xxx)	x.xx (x.xxx-x.xxx)	x.xx (x.xxx-x.xxx)

Tables with similar format:

**Table 90: Correlation of ASC IgG Count vs ALS IgG Titers GMFR by Time Point and Treatment Group, Per Protocol Population**

## 14.3 Safety Data

### 14.3.1 Displays of Adverse Events

**Table 91: Overall Summary of Adverse Events - Oral & Sublingual Cohorts**

	Cohort A: Oral 5 µg dmLT (N=X)		Cohort B: Oral 25 µg dmLT (N=X)		All Oral Cohorts: Placebo (N=X)		All Oral Route Subjects (N=X)		Cohort C: Sublingual 5 µg dmLT (N=X)		Cohort D: Sublingual 25 µg dmLT (N=X)		All Sublingual Cohorts: Placebo (N=X)		All Sublingual Route Subjects (N=X)	
Subjects a with	n	%	n	%	n	%	n	%	n	%	n	%	n	%	n	%
At least one local solicited adverse event	x	x	x	x	x	x	x	x	x	x	x	x	x	x	x	x
At least one systemic solicited adverse event	x	x	x	x	x	x	x	x	x	x	x	x	x	x	x	x
At least one unsolicited adverse event	x	x	x	x	x	x	x	x	x	x	x	x	x	x	x	x
At least one related unsolicited adverse event, through 28 days after the last dose	x	x	x	x	x	x	x	x	x	x	x	x	x	x	x	x
Mild (Grade 1)	x	x	x	x	x	x	x	x	x	x	x	x	x	x	x	x
Moderate (Grade 2)	x	x	x	x	x	x	x	x	x	x	x	x	x	x	x	x
Severe (Grade 3)	x	x	x	x	x	x	x	x	x	x	x	x	x	x	x	x
Not yet assessed																
At least one related unsolicited adverse event, from first vaccination through 6 months after the last dose	x	x	x	x	x	x	x	x	x	x	x	x	x	x	x	x
Mild (Grade 1)	x	x	x	x	x	x	x	x	x	x	x	x	x	x	x	x
Moderate (Grade 2)	x	x	x	x	x	x	x	x	x	x	x	x	x	x	x	x
Severe (Grade 3)	x	x	x	x	x	x	x	x	x	x	x	x	x	x	x	x
Not yet assessed																

	Cohort A: Oral 5 µg dmLT (N=X)		Cohort B: Oral 25 µg dmLT (N=X)		All Oral Cohorts: Placebo (N=X)		All Oral Route Subjects (N=X)		Cohort C: Sublingual 5 µg dmLT (N=X)		Cohort D: Sublingual 25 µg dmLT (N=X)		All Sublingual Cohorts: Placebo (N=X)		All Sublingual Route Subjects (N=X)	
Subjects a with	n	%	n	%	n	%	n	%	n	%	n	%	n	%	n	%
At least one severe (Grade 3) unsolicited adverse event	x	x	x	x	x	x	x	x	x	x	x	x	x	x	x	x
Related	x	x	x	x	x	x	x	x	x	x	x	x	x	x	x	x
Unrelated	x	x	x	x	x	x	x	x	x	x	x	x	x	x	x	x
At least one serious adverse event b	x	x	x	x	x	x	x	x	x	x	x	x	x	x	x	x
At least one related, serious adverse event	x	x	x	x	x	x	x	x	x	x	x	x	x	x	x	x
At least one adverse event leading to early termination c	x	x	x	x	x	x	x	x	x	x	x	x	x	x	x	x
Study withdrawal for any reason	x	x	x	x	x	x	x	x	x	x	x	x	x	x	x	x
Discontinuation of study vaccination for any reason	x	x	x	x	x	x	x	x	x	x	x	x	x	x	x	x

N = Number of subjects in the Safety Population

a Subjects are counted once for each category regardless of the number of events.b A listing of Serious Adverse Events is included in Table 122.c As reported on the Adverse Event eCRF.

Tables with similar format:

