4 STUDY DESIGN

This is an outpatient Phase 1 double-blinded, placebo-controlled, dose-escalation trial in approximately 135 (plus any additional participants if needed to have minimal evaluable participants / cohort as described in [Table 1](#)) apparently healthy adult volunteers, age 18-45 years, who meet all the eligibility criteria and reside in Bangladesh, an endemic country for ETEC infection. The study population will be recruited from Mirpur, a densely populated urban slum community of Dhaka, Bangladesh, known as having a high rate of diarrheal, respiratory and enteric disease.

This clinical trial is designed to assess the safety, reactogenicity, tolerability, and immunogenicity of a range of dosages of dmLT administered by three different routes: oral, SL, or ID. The schematic of study design is presented in [Table 1](#). The oral and SL routes of administration will evaluate dosages of 5, 25, and 50 μ g of dmLT; the ID route of administration will evaluate dosages of 0.3, 1.0, and 2.0 μ g of dmLT. Participants will receive a total of three sequential doses of dmLT; the oral and SL routes will be at days 1, 15, and 29 and the ID route will be at days 1, 22, and 43. After each dose of study product, participants will be observed for 30-90 minutes, depending on the route of administration.

Safety, reactogenicity, and tolerability of the study products will be evaluated for each participant. Solicited local and systemic reactogenicity will be collected for 7 days after each vaccine administration. Memory Aids and digital thermometers will be given to participants to record solicited local and systemic reactogenicity including elevated body temperature (i.e., fever) at home, and they will be reviewed with the participants. Unsolicited AEs will be collected from the time of each study vaccination through 28 days after the last vaccination. Safety laboratories will be collected on Visit 7 or about 28 days after the last vaccination. Serious adverse events (SAEs) will be collected from the time of the first study vaccination through 6 months after the last study vaccination. Tolerability of the study products will be assessed by recording the occurrence of and reason for study withdrawals and discontinuation of study vaccination during the study.

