##### 3.2.2. Secondary Outcome Measures

The **Secondary Safety Endpoints** to be used to evaluate the safety of this study are:

- The occurrence of vaccine-related serious adverse events (SAE) from the first vaccination through 6 months after the last dose of vaccine was administered
-

The **Secondary Immunogenicity Endpoints** to be used to evaluate the immune response to vaccination consist of the following:

- At any time after vaccination, the proportion of participants with a  $\geq 4$ -fold rise in dmLT-specific serum IgG and IgA titers over baseline measured by Enzyme-Linked Immunosorbent Assay (ELISA)
- At any time after vaccination the proportion of participants with  $\geq 8$  dmLT-specific IgA or IgG ASC /  $10^6$  peripheral blood mononuclear cells (PBMC) as measured by Enzyme-Linked ImmunoSpot Assay (ELISpot)
- At any time after vaccination, the proportion of participants with  $\geq 2$ -fold rise in ALS anti-dmLT-specific IgG and IgA titers over baseline measured by ELISA
- At any time after vaccination, the proportion of participants with a  $\geq 4$ -fold rise over baseline in dmLT-specific fecal IgA titers measured by ELISA
- At any time after vaccination, the proportion of participants with a  $\geq 4$ -fold rise over baseline in dmLT-specific salivary IgA titers measured by ELISA

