### 9.5.1 Immunogenicity and Safety Measurements Assessed and Flow Chart

**Table 2: Schedule of Study Procedures – Oral & Sublingual Cohorts**

Oral and Sublingual cohorts												Unscheduled visit, upon investigator judgement	Early Termination 
Study Visit (V)	screen	1	2	3	4	5	6	7	8	9			
Study Day	-7 to -4	1	8	15	22	29	36	57	114	209			
Window			±1d	±2d	±1d	±2d	±1d	±3d	±1w	±2w			
Study Week		0	1	2	3	4	5	8	16	30			
Informed Consent	X												
Confirm Ongoing Consent		X	X	X	X	X	X	X	X	X			
Eligibility Review	X	X	X	X	X	X	X	X	X				
Collection of demographics	X												
Medical History	X	X	X	X	X	X	X	X	X	X		[X]	
Concomitant Medications	X	X	X	X	X	X	X	X	X	X		[X]	
Physical Exam	X	X 			[X]								
Vitals Signs	X 		[X]										
Urine pregnancy test 	X	X		X		X							
VACCINATION		#1		#2		#3							
Pre-vaccination & Post-vaccination assessment		X 		X 		X 							
Memory Aid and thermometer (d)istribute, (c)ollect Memory Aid		d	C	d	C	D	c					[c] 	
Confirm date & time of next Visit		X	X	X	X	X	X	X	X				
Adverse Event (AE)/Serious AE review		X	X 	X	X 	X	X 	X 	X 	X 	X 	X	
Screening stool	X												
Saliva/Oral Fluid for Ab		X	X	X	X	X	X	X					
Stool for ELISA Ab		X	X	X	X	X	X	X					
Stool for future use (Microbiome studies)	X	X	X	X	X	X	X	X					
Clinical labs/chemistry	2 mL							2 mL	2 mL				
Blood-Serum for ELISA Ab & Neut.		3 mL	2 mL	3 mL	2 mL								

*Also may occur:  
Stool culture when indicated;  
Exam and Photo of local reactogenicity when indicated*

Oral and Sublingual cohorts											
Blood-PBMC for ASC		2 mL	2 mL	2 mL	2 mL	2 mL	2 mL				
Blood-PBMC for ASC w/ homing			2 mL		2 mL		2 mL				
Blood-PBMC for ALS		2 mL	2 mL	2 mL	2 mL	2 mL	2 mL				
Blood-PBMC for Memory B assays		8mL			5 mL		5 mL	5 mL	5 mL		
Blood-PBMC for effector T cell assays	13 mL				8mL		7 mL	7 mL	8 mL	10 mL	
Store plasma from PBMC		X	X		X		X	X	X	X	
Total Blood Volume up to ~140 mL/participant	15 mL	15 mL	8 mL	6 mL	21 mL	6 mL	22 mL	17 mL	15 mL	15 mL	10 mL

[ ] Make every effort to collect at Early Termination visit. If not collected, this will not result in a protocol deviation.

review for Serious Adverse Events only

Targeted physical examination, if indicated based on review of medical history

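### SAP Tables 91 and 92 label related unsolicited adverse events by grade as running to 6 months, but non-serious events are systematically collected only to 28 days after the last dose

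*SAP*

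**What the plan says.** SAP Table 91 has two blocks for related unsolicited adverse events, each with lines for mild, moderate and severe. The first is "At least one related unsolicited adverse event, through 28 days after the last dose". The second is "At least one related unsolicited adverse event, from first vaccination through 6 months after the last dose". A separate row further down reads "At least one related, serious adverse event". None of the table's three footnotes limits the second block. Table 92, for the intradermal and pooled columns, is introduced by "Tables with similar format" and a note that changes only the columns, so it inherits both blocks.

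The collection windows are set elsewhere. Protocol section 4 says "Unsolicited AEs will be collected from the time of each study vaccination through 28 days after the last vaccination" and, for serious events, "Serious adverse events (SAEs) will be collected from the time of the first study vaccination through 6 months after the last study vaccination". SAP section 3.2.2 makes the second window a secondary endpoint: "The occurrence of vaccine-related serious adverse events (SAE) from the first vaccination through 6 months after the last dose of vaccine was administered". In the visit schedule (Protocol Appendix A; SAP Tables 2 and 3), the adverse event review at Visits 8 and 9 carries the footnote "review for Serious Adverse Events only".

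**The concern.** The block promises a window that the design delivers for serious events only. SAP section 9.3 makes the denominator of adverse event incidence the total population. A participant who was not systematically asked about non-serious events after day 28 is therefore counted as having had none.

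One of the trial's secondary objectives is long-term safety to 6 months after the last dose. In the overall safety summary, grade lines that barely differ between the 28-day and 6-month blocks invite the conclusion that almost no mild or moderate related events arose later. The trial did not collect the data for that conclusion.

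**Working it through.** **Inputs**
- Day of dose 3: Day 29 oral and sublingual, Day 43 intradermal (Protocol Table 1).
- End of collection for related non-serious unsolicited events: Day 57 oral and sublingual, Day 71 intradermal (SAP 4.5.1, item 4).
- End of collection for related serious events: Day 209 and Day 223 (SAP 4.5.1, item 5).
- Visits not held: Cohort D Visits 8 and 9; Cohort E Visits 6 to 9, with no third dose (SAP section 15).

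**The plan's own cut-offs, reproduced**
- Oral and sublingual: 29 + 28 = 57 and 29 + 180 = 209.
- Intradermal, as planned: 43 + 28 = 71 and 43 + 180 = 223.

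All four match the SAP.

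**Length of the gap on the planned schedule**
- Oral and sublingual: 209 − 57 = 152 days.
- Intradermal: 223 − 71 = 152 days.
- Share of the period after dose 3: 152 / 180 = 84%.

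**Sources that can feed the 6-month block after day 28**
1. Scheduled visits. Protocol 7.3.7 and 7.4.1 ask only about serious events at Visits 8 and 9.
2. Unscheduled visits. Protocol 7.6 takes non-serious information only within 28 days of the last vaccination, and serious information at any time.
3. Definition. Protocol 9.1 describes unsolicited events as related non-serious events to 28 days after the third dose. Read that way, the 6-month block could only repeat the 28-day block. The SAP's displays are wider: Listing 22, for unsolicited events, has a column marking serious events, and Table 139 needs a non-serious qualifier. Read that way, late related serious events enter the block.

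On the wider reading, which is the more favourable to the table:

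6-month count = 28-day count + participants whose only related unsolicited event is a serious event after day 28, or a late event that was volunteered unsystematically.

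Late related serious events are the secondary endpoint and already have their own row.

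**What was actually followed**
- Cohort D: the last scheduled visit not listed as missed is Visit 7, Day 57, which is 57 − 29 = 28 days after dose 3.
- Cohort E: the last dose was on Day 22, and 22 + 28 = 50 is the day of Visit 6, which was not held. SAP 9.7 lists vital signs for this route only to Day 29, and 29 − 22 = 7 days after the last dose.

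Scheduled visits in these two cohorts therefore did not reach 6 months, even for serious events. The same shortfall enters the sublingual placebo column, the pooled sublingual and intradermal columns and the all-subjects column.

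**The case against.** The strongest reply is that the block is redundant rather than misleading. Each endpoint has its own row: related unsolicited events to 28 days (primary) and related serious events (secondary). The windows are stated in SAP 4.5.1 and in the footnotes to the schedule. The shells are empty, and no text draws a conclusion about late mild events. All of that is correct and limits the severity. It does not make the row label true, and a summary table is often read without section 4.5.1 beside it.

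Three stronger readings are tempting, and the documents do not support them:
- A reader might infer that the block reports events that were never collected, or that its mild and moderate lines have no data source. Non-serious events to day 28 and related serious events to 6 months are collected and can enter it. Serious events are also graded for severity. Protocol 9.1 and 9.2.4 make the investigator responsible for all events observed or reported during the study, and SAP 9.3 includes every reported event. A volunteered late event could therefore be in the database. What is missing is systematic enquiry about non-serious events arising after day 28.
- A reader might infer that lasting pigment change after intradermal dosing would be missed. Pigment change is a solicited local event for that route, and Protocol 9.4 follows adverse events until resolved or stable. Persistence of an early event does not depend on new collection after day 28.
- A reader might take the intradermal gap as observed follow-up. It describes the planned schedule, which Cohort E did not complete.

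The objection also shows that simply labelling the related-serious-event row as running to 6 months would repeat the overstatement for Cohorts D and E. That point stands, and the fix below allows for it.

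**Conclusion.** The plan is wrong as written on this point. The 6-month block combines a 28-day window for non-serious events with a 6-month window for serious ones, under a label that claims 6 months for both. Its mild and moderate lines are not 6-month rates. Read as such, they can only be too low, because 152 of the 180 days after dose 3 have no systematic collection of non-serious events. How much too low cannot be stated, since the documents give no rate of late non-serious events.

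This rests on three assumptions: Table 92 follows the layout of Table 91; unsolicited events in the SAP's tables include serious ones, as Listing 22 implies; and no contacts outside the visit schedule replaced the missed visits. The documents do not say whether serious events were sought another way in Cohorts D and E. No primary or secondary endpoint estimate changes. The defect lies in what the safety summary appears to show about long-term safety.

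**What to change.** In Tables 91 and 92:
1. Remove the 6-month block of related unsolicited events and its grade lines. Keep the 28-day block.
2. State the intended window, first vaccination to 6 months after the last dose, on the existing row for related serious events.
3. Add a footnote that non-serious events were systematically collected only through 28 days after the last dose, and that any later volunteered events appear in Listing 22.
4. Add a footnote that Cohort D had no Visits 8 and 9, and that Cohort E had no third dose and no Visits 6 to 9. It should say that scheduled follow-up in the Cohort D, Cohort E and affected pooled columns did not reach 6 months, and give the follow-up actually achieved for each. If serious events were sought by other contacts, say so there.

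The cost is an edit to two table shells plus a follow-up summary from dates already recorded. No new data are needed. The stated scope of the long-term safety summary becomes slightly narrower, which matches what was observed.

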**Table 92: Overall Summary of Adverse Events - Intradermal & Pooled Cohorts**

*[Implementation note: Treatment groups are Cohort E: Intradermal 0.3 µg dmLT (N=X), Cohort E: Intradermal Placebo (N=X), and All Intradermal Route Subjects (N=X). All Subjects (N=X) will be added at the end.]*

**Table 93: Adverse Events Occurring in 5% of Subjects in Any Treatment Group by MedDRA System Organ Class and Preferred Term, and Treatment Group – Oral & Sublingual Cohorts**

MedDRA Preferred Term	MedDRA System Organ Class	Cohort A: Oral 5 µg dmLT (N=X)			Cohort B: Oral 25 µg dmLT (N=X)			All Oral Cohorts: Placebo (N=X)			All Oral Route Subjects (N=X)			Cohort C: Sublingual 5 µg dmLT (N=X)			Cohort D: Sublingual 25 µg dmLT (N=X)			All Sublingual Cohorts: Placebo (N=X)			All Sublingual Route Subjects (N=X)						
		n	%	Events	n	%	Events	n	%	Events	n	%	Events	n	%	Events	n	%	Events	n	%	Events	n	%	Events	n	%	Events	
Serious Adverse Events																													
All	All	x	x	x	x	x	x	x	x	x	x	x	x	x	x	x	x	x	x	x	x	x	x	x	x	x	x		
PT1	SOC1	x	x	x	x	x	x	x	x	x	x	x	x	x	x	x	x	x	x	x	x	x	x	x	x	x	x		
Etc.	Etc.																												
Other (Non-serious) Adverse Events																													
All	All	x	x	x	x	x	x	x	x	x	x	x	x	x	x	x	x	x	x	x	x	x	x	x	x	x	x		
PT1	SOC1	x	x	x	x	x	x	x	x	x	x	x	x	x	x	x	x	x	x	x	x	x	x	x	x	x	x		
Etc.	Etc.																												

N = number of subjects in the Safety Population (number of subjects at risk).

n= number of subjects reporting event.

Events= total frequency of events reported.

Tables with similar format:

**Table 94: Adverse Events Occurring in 5% of Subjects in Any Treatment Group by MedDRA System Organ Class and Preferred Term, and Treatment Group – Intradermal & Pooled Cohorts**

*[Implementation note: Treatment groups are Cohort E: Intradermal 0.3 µg dmLT (N=X), Cohort E: Intradermal Placebo (N=X), and All Intradermal Route Subjects (N=X). All Subjects (N=X) will be added at the end.]*

**Table 95: Serious Adverse Events by MedDRA System Organ Class and Preferred Term, and Treatment Group – Oral & Sublingual Cohorts****Table 96: Serious Adverse Events by MedDRA System Organ Class and Preferred Term, and Treatment Group – Intradermal & Pooled Cohorts**

*[Implementation note: Treatment groups are Cohort E: Intradermal 0.3 µg dmLT (N=X), Cohort E: Intradermal Placebo (N=X), and All Intradermal Route Subjects (N=X). All Subjects (N=X) will be added at the end.]*

**14.3.1.1      Solicited Adverse Events****Table 97:      Number and Percentage of Subjects Experiencing Solicited Events with 95% Confidence Intervals by Symptom, Dose, and Treatment Group – Cohort A: Oral 5 µg dmLT**

Symptom	Post Dose 1 (N=X)			Post Dose 2 (N=X)			Post Dose 3 (N=X)			Post Any Dose (N=X)		
	n	%	95% CI	n	%	95% CI	n	%	95% CI	n	%	95% CI
Any Symptom	x	xx	x.x, x.x	x	xx	x.x, x.x	x	xx	x.x, x.x	x	xx	x.x, x.x
Any Systemic Symptom												
Fever												
Feverishness												
Fatigue												
Malaise												
Myalgia												
Headache												
Any Local Symptom												
Irritation of the Oral Cavity or Tongue												
Diarrhea												
Nausea												
Vomiting												
Abdominal Discomfort												

Note: N=Number of subjects in the Safety Population

Tables with similar format:

**Table 98:      Number and Percentage of Subjects Experiencing Solicited Events with 95% Confidence Intervals by Symptom, Dose, and Treatment Group – Cohort B: Oral 25 µg dmLT****Table 99:      Number and Percentage of Subjects Experiencing Solicited Events with 95% Confidence Intervals by Symptom, Dose, and Treatment Group – All Oral Cohorts: Placebo**

**Table 100: Number and Percentage of Subjects Experiencing Solicited Events with 95% Confidence Intervals by Symptom, Dose, and Treatment Group – Cohort C: Sublingual 5 µg dmLT**

*[Implementation note: Systemic symptoms presented will be fever, feverishness, fatigue, malaise, myalgia, or headache. Local symptoms presented will be irritation of the oral cavity or tongue, facial nerve disturbance, diarrhea, nausea, vomiting, or abdominal discomfort.]*

**Table 101: Number and Percentage of Subjects Experiencing Solicited Events with 95% Confidence Intervals by Symptom, Dose, and Treatment Group – Cohort D: Sublingual 25 µg dmLT**

*[Implementation note: Systemic symptoms presented will be fever, feverishness, fatigue, malaise, myalgia, or headache. Local symptoms presented will be irritation of the oral cavity or tongue, facial nerve disturbance, diarrhea, nausea, vomiting, or abdominal discomfort.]*

**Table 102: Number and Percentage of Subjects Experiencing Solicited Events with 95% Confidence Intervals by Symptom, Dose, and Treatment Group – All Sublingual Cohorts: Placebo**

*[Implementation note: Systemic symptoms presented will be fever, feverishness, fatigue, malaise, myalgia, or headache. Local symptoms presented will be irritation of the oral cavity or tongue, facial nerve disturbance, diarrhea, nausea, vomiting, or abdominal discomfort.]*

**Table 103: Number and Percentage of Subjects Experiencing Solicited Events with 95% Confidence Intervals by Symptom, Dose, and Treatment Group – Cohort E: Intradermal 0.3 µg dmLT**

*[Implementation note: Systemic symptoms presented will be fever, feverishness, fatigue, malaise, myalgia, headache, diarrhea, nausea, vomiting, or abdominal discomfort. Local symptoms presented will be injection site pain, redness, swelling, bruising, itching, hypo/hyper pigmentation and induration, vesicles or hardened mass.]*

**Table 104: Number and Percentage of Subjects Experiencing Solicited Events with 95% Confidence Intervals by Symptom, Dose, and Treatment Group – Cohort E: Intradermal Placebo**

*[Implementation note: Systemic symptoms presented will be fever, feverishness, fatigue, malaise, myalgia, headache, diarrhea, nausea, vomiting, or abdominal discomfort. Local symptoms presented will be injection site pain, redness, swelling, bruising, itching, hypo/hyper pigmentation and induration, vesicles or hardened mass.]*

**Table 105: Number and Percentage of Subjects Experiencing Solicited Events by Symptom, Maximum Severity, Dose – Cohort A: Oral 5 µg dmLT**

Symptom	Severity	Post Dose 1 (N=X)			Post Dose 2 (N=X)			Post Dose 3 (N=X)			Post Any Dose (N=X)		
		n	%	95% CI	n	%	95% CI	n	%	95% CI	n	%	95% CI
Any Symptom	None	x	xx	x.x, x.x	x	xx	x.x, x.x	x	xx	x.x, x.x	x	xx	x.x, x.x
	Mild												
	Moderate												
	Severe												
Systemic Symptoms													
Any Systemic Symptom	None												
	Mild												
	Moderate												
	Severe												
Fever	None												
	Mild												
	Moderate												
	Severe												
Feverishness	None												
	Mild												
	Moderate												
	Severe												
Fatigue	None												
	Mild												
	Moderate												
	Severe												
Malaise	None												
	Mild												

Symptom	Severity	Post Dose 1 (N=X)			Post Dose 2 (N=X)			Post Dose 3 (N=X)			Post Any Dose (N=X)		
		n	%	95% CI	n	%	95% CI	n	%	95% CI	n	%	95% CI
	Moderate												
	Severe												
Myalgia	None												
	Mild												
	Moderate												
	Severe												
Headache	None												
	Mild												
	Moderate												
	Severe												
Local Symptoms													
Any Local Symptom	None												
	Mild												
	Moderate												
	Severe												
Irritation of the Oral Cavity or Tongue	None												
	Mild												
	Moderate												
	Severe												
Diarrhea	None												
	Mild												
	Moderate												
	Severe												

Symptom	Severity	Post Dose 1 (N=X)			Post Dose 2 (N=X)			Post Dose 3 (N=X)			Post Any Dose (N=X)		
		n	%	95% CI	n	%	95% CI	n	%	95% CI	n	%	95% CI
Nausea	None												
	Mild												
	Moderate												
	Severe												
Vomiting	None												
	Mild												
	Moderate												
	Severe												
Abdominal Discomfort	None												
	Mild												
	Moderate												
	Severe												

Note: N = Number of subjects in the Safety Population who received the specified dose. Severity is the maximum severity reported over all solicited symptoms post dosing for each subject.

Tables with similar format:

**Table 106: Number and Percentage of Subjects Experiencing Solicited Events by Symptom, Maximum Severity, Dose – Cohort B: Oral 25 µg dmLT**

**Table 107: Number and Percentage of Subjects Experiencing Solicited Events by Symptom, Maximum Severity, Dose – All Oral Cohorts: Placebo**

**Table 108: Number and Percentage of Subjects Experiencing Solicited Events by Symptom, Maximum Severity, Dose – Cohort C: Sublingual 5 µg dmLT**

*[Implementation note: Systemic symptoms presented will be fever, feverishness, fatigue, malaise, myalgia, or headache. Local symptoms presented will be irritation of the oral cavity or tongue, facial nerve disturbance, diarrhea, nausea, vomiting, or abdominal discomfort.]*

**Table 109: Number and Percentage of Subjects Experiencing Solicited Events by Symptom, Maximum Severity, Dose – Cohort D: Sublingual 25 µg dmLT**

*[Implementation note: Systemic symptoms presented will be fever, feverishness, fatigue, malaise, myalgia, or headache. Local symptoms presented will be irritation of the oral cavity or tongue, facial nerve disturbance, diarrhea, nausea, vomiting, or abdominal discomfort.]*

**Table 110: Number and Percentage of Subjects Experiencing Solicited Events by Symptom, Maximum Severity, Dose – All Sublingual Cohorts: Placebo**

*[Implementation note: Systemic symptoms presented will be fever, feverishness, fatigue, malaise, myalgia, or headache. Local symptoms presented will be irritation of the oral cavity or tongue, facial nerve disturbance, diarrhea, nausea, vomiting, or abdominal discomfort.]*

**Table 111: Number and Percentage of Subjects Experiencing Solicited Events by Symptom, Maximum Severity, Dose – Cohort E: Intradermal 0.3 µg dmLT**

*[Implementation note: Systemic symptoms presented will be fever, feverishness, fatigue, malaise, myalgia, headache, diarrhea, nausea, vomiting, or abdominal discomfort. Local symptoms presented will be injection site pain, redness, swelling, bruising, itching, hypo/hyper pigmentation and induration, vesicles or hardened mass.]*

**Table 112: Number and Percentage of Subjects Experiencing Solicited Events by Symptom, Maximum Severity, Dose – Cohort E: Intradermal Placebo**

*[Implementation note: Systemic symptoms presented will be fever, feverishness, fatigue, malaise, myalgia, headache, diarrhea, nausea, vomiting, or abdominal discomfort. Local symptoms presented will be injection site pain, redness, swelling, bruising, itching, hypo/hyper pigmentation and induration, vesicles or hardened mass.]*

**Table 113: Number and Percentage of Subjects Experiencing Solicited Events by Symptom, Severity, Dose, Day Post Dosing, and Treatment Group – Cohort A: Oral 5 µg dmLT, Dose 1**

Symptom	Severity	Pre-Dose		Post-Dose		Day 1		Day 2		Day 3		Day 4		Day 5		Day 6		Day 7	
		n	%	n	%	n	%	n	%	n	%	n	%	n	%	n	%	n	%
Any Symptom	None	x	xx	x	xx	x	xx	x	xx	x	xx	x	xx	x	xx	x	xx	x	xx
	Mild																		
	Moderate																		
	Severe																		
	Not Reported																		
Systemic Symptoms																			
Any Systemic Symptom	None	x	xx	x	xx	x	xx	x	xx	x	xx	x	xx	x	xx	x	xx	x	xx
	Mild																		
	Moderate																		
	Severe																		
	Not Reported																		
Fever	None																		
	Mild																		
	Moderate																		
	Severe																		
	Not Reported																		
Feverishness	None																		
	Mild																		
	Moderate																		
	Severe																		
	Not Reported																		
Fatigue	None																		
	Mild																		
	Moderate																		
	Severe																		
	Not Reported																		

Symptom	Severity	Pre-Dose		Post-Dose		Day 1		Day 2		Day 3		Day 4		Day 5		Day 6		Day 7	
		n	%	n	%	n	%	n	%	n	%	n	%	n	%	n	%	n	%
	Mild																		
	Moderate																		
	Severe																		
	Not Reported																		
Malaise	None																		
	Mild																		
	Moderate																		
	Severe																		
	Not Reported																		
Myalgia	None																		
	Mild																		
	Moderate																		
	Severe																		
	Not Reported																		
Headache	None																		
	Mild																		
	Moderate																		
	Severe																		
	Not Reported																		
Local Symptoms																			
Any Local Symptom	None	x	xx	x	xx	x	xx	x	xx	x	xx	x	xx	x	xx	x	xx	x	
	Mild																		
	Moderate																		
	Severe																		
	Not Reported																		

Symptom	Severity	Pre-Dose		Post-Dose		Day 1		Day 2		Day 3		Day 4		Day 5		Day 6		Day 7	
		n	%	n	%	n	%	n	%	n	%	n	%	n	%	n	%	n	%
Irritation of the Oral Cavity or Tongue	None																		
	Mild																		
	Moderate																		
	Severe																		
	Not Reported																		
Diarrhea	None																		
	Mild																		
	Moderate																		
	Severe																		
	Not Reported																		
Nausea	None																		
	Mild																		
	Moderate																		
	Severe																		
	Not Reported																		
Vomiting	None																		
	Mild																		
	Moderate																		
	Severe																		
	Not Reported																		
Abdominal Discomfort	None																		
	Mild																		
	Moderate																		

Symptom	Severity	Pre-Dose		Post-Dose		Day 1		Day 2		Day 3		Day 4		Day 5		Day 6		Day 7	
		n	%	n	%	n	%	n	%	n	%	n	%	n	%	n	%	n	%
	Severe																		
	Not Reported																		

Note: N = Number of subjects in the Safety Population who received the specified dose. Severity is the maximum severity reported post dosing for each subject for each day.

Tables with similar format:

**Table 114:** Number and Percentage of Subjects Experiencing Solicited Events by Symptom, Severity, Dose, Day Post Dosing, and Treatment Group – Cohort A: Oral 5 µg dmLT, Dose 2

**Table 115:** Number and Percentage of Subjects Experiencing Solicited Events by Symptom, Severity, Dose, Day Post Dosing, and Treatment Group – Cohort A: Oral 5 µg dmLT, Dose 3

**Table 116:** Number and Percentage of Subjects Experiencing Solicited Events by Symptom, Severity, Dose, Day Post Dosing, and Treatment Group – Cohort B: Oral 25 µg dmLT, Dose 1

**Table 117:** Number and Percentage of Subjects Experiencing Solicited Events by Symptom, Severity, Dose, Day Post Dosing, and Treatment Group – Cohort B: Oral 25 µg dmLT, Dose 2

**Table 118:** Number and Percentage of Subjects Experiencing Solicited Events by Symptom, Severity, Dose, Day Post Dosing, and Treatment Group – Cohort B: Oral 25 µg dmLT, Dose 3

**Table 119:** Number and Percentage of Subjects Experiencing Solicited Events by Symptom, Severity, Dose, Day Post Dosing, and Treatment Group – All Oral Cohorts: Placebo, Dose 1

**Table 120:** Number and Percentage of Subjects Experiencing Solicited Events by Symptom, Severity, Dose, Day Post Dosing, and Treatment Group – All Oral Cohorts: Placebo, Dose 2

**Table 121:** Number and Percentage of Subjects Experiencing Solicited Events by Symptom, Severity, Dose, Day Post Dosing, and Treatment Group – All Oral Cohorts: Placebo, Dose 3

**Table 122:** Number and Percentage of Subjects Experiencing Solicited Events by Symptom, Severity, Dose, Day Post Dosing, and Treatment Group – Cohort C: Sublingual 5 µg dmLT, Dose 1

*[Implementation note: Systemic symptoms presented will be fever, feverishness, fatigue, malaise, myalgia, or headache. Local symptoms presented will be irritation of the oral cavity or tongue, facial nerve disturbance, diarrhea, nausea, vomiting, or abdominal discomfort.]*

**Table 123: Number and Percentage of Subjects Experiencing Solicited Events by Symptom, Severity, Dose, Day Post Dosing, and Treatment Group – Cohort C: Sublingual 5 µg dmLT, Dose 2**

*[Implementation note: Systemic symptoms presented will be fever, feverishness, fatigue, malaise, myalgia, or headache. Local symptoms presented will be irritation of the oral cavity or tongue, facial nerve disturbance, diarrhea, nausea, vomiting, or abdominal discomfort.]*

**Table 124: Number and Percentage of Subjects Experiencing Solicited Events by Symptom, Severity, Dose, Day Post Dosing, and Treatment Group – Cohort C: Sublingual 5 µg dmLT, Dose 3**

*[Implementation note: Systemic symptoms presented will be fever, feverishness, fatigue, malaise, myalgia, or headache. Local symptoms presented will be irritation of the oral cavity or tongue, facial nerve disturbance, diarrhea, nausea, vomiting, or abdominal discomfort.]*

**Table 125: Number and Percentage of Subjects Experiencing Solicited Events by Symptom, Severity, Dose, Day Post Dosing, and Treatment Group – Cohort D: Sublingual 25 µg dmLT, Dose 1**

